ClinicalTrials.gov Identifier: NCT03082313

Date uploaded 10/20/21

Version 02/10/18

Leg Movement Rate before and after a Caregiver- Provided Intervention for Infants at Risk of Developmental Disability: A Pilot Study

Protocol: Intervention: Leg Movement Rate

Significance

Infants with developmental delay often experience lifelong functional limitations in motor, cognitive and social domains. A strictly-defined, conservative estimate recently determined that ~9% of infants in the US are eligible for early intervention services because they are at risk for developmental delay. Diagnoses of developmental delay are typically made at 18 to 24 months of age¹ and current practice is to provide infrequent, low intensity therapies or no intervention across infancy²⁻⁴. In infants born preterm, for example, low intensity developmental interventions have generally demonstrated short-term benefits that are not sustained into the school years⁵⁻⁸. Basic science evidence supports that early and intense therapy intervention is more effective at promoting optimal neuromotor structure and function⁹⁻¹¹. Given this information, dosing of pediatric physical therapy intervention is a current topic of high interest in the field¹², and researchers are starting to investigate the feasibility of different approaches for providing early, intense interventions^{13,14}. Although these approaches are laudable and strongly theoretically based there is a fundamental gap: we do not know what amount and type of movement experience is necessary and sufficient to have a positive effect on the development of infant neuromotor control. This proposal will address this fundamental question by increasing the leg movement experience of infants at risk for developmental delay to an evidence-based minimum threshold for quantity and type of movement and measuring the association between amount of leg movement experience and motor development rate.

The intervention promotes movement experience from 3 months to sitting onset, based on our pilot data that indicate infants at risk for developmental delay who demonstrate a leg movement rate below 1200 movements per hour of awake time across a day are more likely to have a poor neuromotor outcome than infants who demonstrate a leg movement rate above 1200 movements per hour of awake time. Further, infants at risk for developmental delay move their legs significantly less and make a higher proportion of unilateral movements than infants with typical development. The goal of the intervention is to increase infant movement experience above the quantity threshold while consisting of the prescribed type (1200 movements per hour of awake time with variety of type of movement) in order to provide sufficient and necessary experience for learning neuromotor control.

Approach

Recruitment. Participants will be a representative sample of 12 infants AR recruited using 4 methods. 1) The infants will be recruited with fliers placed around USC campuses and public spaces such as local libraries. Fliers will also be distributed in person and/or electronically via email to local early intervention providers, on social media sites including facebook and instagram, and on the website of the Division of Biokinesiology and Physical Therapy. The parent or legal guardian will be asked to contact research staff by phone or email for further information about the research study, including further discussion of the inclusion criteria. When the parent or legal guardian contacts research staff, the research staff will give more specific information about the study and answer any questions. If they choose to participate after the initial contact, a written consent form will be mailed to them. This will allow the parents and/or legal guardians to discuss their participation with others before signing the written consent. 2) A licensed healthcare provider at CHLA or an early intervention provider, with the permission of the parent or legal guardian, will provide the research staff with the name and phone number of the parent of a potential infant participant who is under their professional care. Research staff will call the parent or legal guardian and give more specific information about the study and answer any

questions. If they choose to participate after the initial contact, a written consent form will be mailed to them. This will allow the parents and/or legal guardians to discuss their participation with others before signing the written consent. 3) Research staff will attend the High Risk Follow-Up Clinic at CHLA. A licensed healthcare provider at CHLA, with the permission of the parent or legal guardian, will introduce the research staff to the family. The research staff will give more specific information about the study and answer any questions. If they choose to participate after the initial contact, a written consent form will be mailed to them. This will allow the parents and/or legal guardians to discuss their participation with others before signing the written consent. 4) A CHLA Clinical Research Coordinator (CRC) will coordinate with the High Risk Follow Up Clinic and potentially the NICU to review infants' medical records for eligibility and speak to families of potential participants. With the permission of the parent or legal guardian, the CRC will provide the research staff with the contact info. Research staff will call the parent or legal guardian and give more specific information about the study and answer any questions. If they choose to participate after the initial contact, a written consent form will be mailed to them. This will allow the parents and/or legal guardians to discuss their participation with others before signing the written consent.

Inclusion Criteria. Infants will be 3-6 months of adjusted age at the first visit, +/- 30 days. Infants will be defined as at risk in accordance with the definition below (confirmed by the PI or the CHLA CRC) ¹⁵:

CCS HRIF PROGRAM MEDICAL ELIGIBILITY CRITERIA

UPDATED 01/2017

Data should be collected on infants/children under three years of age who meet California Children's Services (CCS) HRIF medical eligibility criteria **and** who met CCS medical eligibility criteria for Neonatal Intensive Care Unit (NICU) care **OR** had a CCS eligible medical condition at some time during their stay in a CCS-approved NICU, even if they were never a CCS client. **Infants are medically eligible for the HRIF Program when the infant:**

Met CCS medical eligible criteria for NICU care, in a CCS Program-approved NICU, regardless of length of stay, (as per Number Letter 05-0502, Medical Eligibility in a CCS Program-approved NICU or the most current N.L.). **NOTE:** Medical eligibility includes neonates who require direct admit to a CCS-approved PICU, who are never admitted to a CCS Program-approved NICU, but who otherwise meet all medical eligibility criteria for HRIF services.

OR **Had a CCS Program-eligible medical condition in a CCS Program-approved NICU, regardless of length of stay, even if they were never CCS Program Clients during their stay, (as per California Code of Regulations, Title 22, Section 41515.1 through 41518.9, CCS Program Medical Eligibility Regulations).**

AND MET ONE OF THE FOLLOWING:

Birth weight ≤ 1500 grams or the gestational age at birth < 32 weeks.

OR

Birth weight > 1500 grams and the gestational age at birth ≥ 32 weeks and one of the following criteria was met during the NICU stay:

HRIF Program Referral Process:

Communication is between the CCS Program-approved NICU and HRIF Program.

1. The discharging/referring NICU/Hospital will refer eligible infants to the HRIF Program at the time of discharge to home, and complete the "Referral/Registration (RR) Form" via the web-based HRIF-QCI Reporting System.
2. The discharging/referring NICU/Hospital or HRIF Program will submit a Service Authorization Request (SAR) to the local CCS Office for HRIF Services. (Service Code Group [SCG] 06, should be requested).
<http://www.dhcs.ca.gov/services/ccs/cmsnet/Pages/SARTools.aspx>
3. The discharging/referring NICU/Hospital will send a copy of the Discharge Summary to the HRIF Program.

1. pH less than 7.0 on an umbilical blood sample or a blood gas obtained within one hour of life) or an Apgar score of less than or equal to three at five minutes or an Apgar score less than 5 at 10 minutes.
2. An unstable infant manifested by hypoxia, acidemia, hypoglycemia and/or hypotension requiring pressor support.
3. Persistent apnea which required caffeine or other stimulant medication for the treatment of apnea at discharge.
4. Required oxygen for more than 28 days of hospital stay and had radiographic finding consistent with chronic lung disease (CLD).
5. Infants placed on extracorporeal membrane oxygenation (ECMO).
6. Infants who received inhaled nitric oxide greater than four hours, and/or treatment during hospitalization with sildenafil or other pulmonary vasodilatory medications for pulmonary hypertension.
7. Congenital heart disease requiring surgery or minimally invasive intervention.
8. History of observed clinical or electroencephalographic (EEG) seizure activity or receiving antiepileptic medication(s) at time of discharge.
9. Evidence of intracranial pathology, including but not limited to, intracranial hemorrhage (grade II or worse), white matter injury including periventricular leukomalacia (PVL), cerebral thrombosis, cerebral infarction or stroke, congenital structural central nervous system (CNS) abnormality or other CNS problems associated with adverse neurologic outcome.
10. Clinical history and/or physical exam findings consistent with neonatal encephalopathy.
11. Other documented problems that could result in neurologic abnormality, such as: history of CNS infection, documented sepsis, bilirubin at excessive levels concerning for brain injury as determined by NICU medical staff, history of cardiovascular instability as determined by NICU medical staff due to: sepsis, congenital heart disease, patent ductus arteriosus (PDA), necrotizing enterocolitis, other documented conditions.

Medical eligibility for the HRIF Program is determined by the County CCS Program or Regional Office staff. The CCS Program is also required to determine residential eligibility. As the HRIF Program is a diagnostic service, there is no financial eligibility determination performed at the time of referral to CCS. However, insurance information shall be obtained by CCS. An infant or child is eligible for the HRIF Program from birth up to 3 years of age.

Exclusion Criteria. Infants with congenital malformations of the legs will be excluded.

Procedures. A parent or legal guardian will sign an informed consent form prior to their infant's participation. They will receive the consent form to review and will have any questions answered before scheduling a visit. At the time of the visit, they will inspect all equipment and toys have any questions answered before signing the consent form. A caregiver will be present and engaged throughout the data collection visit, which lasts approximately 1 hour in their home, or, if they prefer, in our laboratory. Infants will receive \$20 compensation and souvenir photos for each visit.

Data Collection. All infants will be assessed in their homes once per month (+ or - 5 days), from 3-6 months of corrected age until sitting onset (can maintain independent sitting > 30 s) or 9 months corrected age, whichever occurs first. We have chosen this as our intervention endpoint because 1) once sitting is established, the way in which infants use their legs shifts drastically (from mostly supine and some prone free movement to primary use as postural stability) and 2) if they are not sitting independently by 9 months corrected age it is straightforward clinically to identify significantly delay. The goal of our intervention is to get them on the "right track" early, not to provide intervention once a significant delay has occurred. We have chosen to start our intervention at 3 months of corrected age, as this is just before relationships have been observed between leg movement frequency and later functional outcomes (as described in the significance section). Sensor Data. To record leg movement rate, infants will wear custom leg warmers with a pocket that securely holds a movement sensor at each ankle from the morning visit until bedtime. The caregivers will remove the leg warmers and sensors when they put their infant to bed for the night (~10-12 hours later). We will return to pick them up the next day. Amount and type of leg movements will be determined using our existing, validated software algorithms. Assessments. We will measure the infant's weight, length, head circumference, thigh and shank lengths and circumferences. We will document medical and therapy interventions being received and assess motor skills using the Alberta Infant Motor Scale (AIMS), a standardized, norm-referenced observational scale¹⁶. We will record 5 minutes of spontaneous movement video to have a visual reference for data. We will record the caregiver teaching the child a novel task and assess the caregiver-infant interaction using the Nursing Child Assessment Teaching Scale (NCAT), a evidence based standardized-assessment tool¹⁷.

Intervention. At each visit, the caregiver will be reminded of the infant's movement. The research team will spend 15 minutes interacting with the caregiver to determine possible ways to achieve the goal of 1200 movements per hour of awake time, with a variety of movements. Strategies to increase leg movements will be encouraged based on the infant's developmental level and what they demonstrate a response to, including: shake a toy when infant moves legs, sing a line of a song when infant moves legs, change the position of the infant to encourage more leg movement, or lightly tickle the legs and feet of the infant. The intervention will use the GAME (Goals - Activity - Motor Enrichment) protocol, a motor learning, environmental enrichment intervention that has recently been shown to be effective for improving motor skills in infants at high risk of cerebral palsy compared to standard care. The intervention is based on the principles of active motor learning, family centred care, parent coaching and environmental enrichment. Intervention was customised to parent goals and enrichment style and the child's motor ability. To increase the dose of motor practice families were provided with a home program containing suggested activities according to identified goals^{14,18,19}. We are expanding this effective intervention by applying it to a new population (infants broadly at risk as opposed to specifically at risk for cerebral palsy) and by specifically quantifying the dose of leg movement experience (amount and type). Otherwise, all intervention will be consistent with the established, published protocol. A customized logbook of all exercises with demonstration pictures of the baby, instructions, and tracking (amount and type) will be provided to the family each visit. Example Intervention Strategy. The research team and family determine that the baby likes Mom smiling and singing "You are my sunshine". They decide that every time the baby's diaper is changed, Mom will demonstrate by assisting the baby with

producing alternating kicks while smiling and singing for 10 total alternating kicks (5 each leg) and then encouraging the baby to perform alternating kicks (not assisting) for 15 seconds and responding with singing and smiling if he or she does. Five sets will be performed each diaper change. Fidelity. Caregivers will keep logbooks of the amount and type of movement experience they provide. This will assist our efforts to create a manual of intervention strategies for future grant proposals. Despite best intentions, however, logbooks are often incomplete; the GAME study reported ~ 50% completion¹⁹. Our main fidelity measure in this study will be the movement rate and proportion of unilateral movements demonstrated by the infants across days and months. We will be able to compare these data to our existing observational data to measure the intervention effect size.

Follow Up: Families will be contacted by email or phone every 3-4 months from after the last visit until 24 months of corrected age for updates on their child's medical and developmental status.

Statistical test and analyses were performed using SPSS (Version 24; IBM, Corporation, Armonk, NY, USA). We first checked all variables for normality by plotting histograms and visually inspecting the data. Given the sample size and visual inspection of the variables, we chose to analyze our data using non-parametric statistics. The median and range were used to represent all descriptive statistics for the first and last visit. Wilcoxon Signed Ranked tests ($\alpha = 0.05$) were used to compare the leg movement rates, adherence, and NCAST-Teaching total score to test for significant differences between the first and last visits. Spearman rank order correlations ($\alpha = 0.05$) were used to test for significant relationships between quality of caregiver-child interaction and adherence to the intervention and leg movement rate at all visits.

Sample size justification. We determined our sample size of 12 for this pilot intervention study based on our observational pilot data. In our pilot data, we found large effect sizes (Cohen's $d = 0.8 - 1.3$) for leg movement quantity (movements per hour of awake time) between 12 infants with TD and 24 infants AR (anticipate ~12 good and ~12 poor neuromotor outcomes). With the planned primary comparison of leg movement of those who received intervention ($N = 12$) versus those who did not ($N = 24$), we should be able to detect an effect of Cohen's d of 1.0 at 9 months, with $\alpha = 0.05$ and 80% power.

Potential Risks

Wearable Sensors: There is a small risk of skin irritation from wearing the legwarmers all day. Parents will be able to visually see their infants' feet at all times (they are not covered) and can remove the legwarmers briefly as desired to inspect their infant's skin. Although the movement sensors are small, they are not small enough to present a choking hazard. They measure 1.4 inches by 1.9 inches, larger than the standard choking hazard guidelines.²⁰

Storage of Materials. There is a small risk of disclosure of participant's personal information. Data collected from participants includes biological data of leg movement activity, video recordings and health status information. All information collected will be kept private and secure. Password protection and secure internal computer networks and REDCap, a HIPAA-compliant database system hosted by USC, will be used to collect and store data. Hard copies of data, including 2 backup copies on external hard drives, will be stored in a locked, waterproof, fireproof safe in a locked room in a secured building (keys, identification cards) on a secured campus (identification cards, security patrol). Unique identifier codes will be used to separate all data collected from any personal identifying information. Laboratory members will have access to data identified by code for analysis and manuscript preparation, while only the PI and Research Assistant (RA) will have access to identifying information for participant tracking purposes.

Intervention. As is typical with trying to get an infant to perform any desired behavior, there is a risk that

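### The primary comparison is powered on 12 treated infants at 9 months, but a treated infant found sitting at an earlier visit has no 9-month recording

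*Combined protocol and SAP*

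**What the plan says.** All of this is in the combined protocol and SAP.

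- **Sample size justification.** The sentence that gives the power begins "With the planned primary comparison of leg movement of those who received intervention" (12 infants) against those who did not (24 infants). The detectable effect is a Cohen's "d of 1.0 at 9 months", with alpha 0.05 and 80% power.
- **Data Collection.** Infants are visited once a month, within 5 days either way, and wear the leg sensors from the visit until bedtime. This continues "until sitting onset (can maintain independent sitting > 30 s) or 9 months corrected age, whichever occurs first". Two reasons are given for that endpoint: "once sitting is established, the way in which infants use their legs shifts drastically", and "if they are not sitting independently by 9 months corrected age it is straightforward clinically to identify significantly delay".
- **Follow Up.** After the last visit, families give updates by email or phone until 24 months corrected age. No further recording is described.
- **Fidelity.** On the infants' movement data: "We will be able to compare these data to our existing observational data to measure the intervention effect size".
- **Statistics paragraph (after Follow Up).** The authors write that "we chose to analyze our data using non-parametric statistics". Wilcoxon tests are used to "compare the leg movement rates, adherence, and NCAST-Teaching total score to test for significant differences between the first and last visits", and Spearman correlations cover caregiver interaction, adherence and leg movement rate. There is no treated-versus-untreated test.

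**The concern.** The power statement and the stopping rule do not fit together. The power statement counts 12 treated infants with a value at 9 months. The stopping rule ends recording for any infant found sitting at an earlier visit, and nothing supplies a 9-month value afterwards. The plan has no extra recording, no substitute value and no allowance for the loss.

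Two things are at stake. First, the stated power has no reserve, so any early sitter lowers it. Second, the loss is not like ordinary dropout: infants leave because they reach a motor milestone, in a study meant to help motor development. The treated infants who remain at 9 months are those not found sitting before that visit, and the protocol itself regards not sitting by then as a mark of delay. The documents do not say at what ages the 24 untreated infants were recorded, or whether their recordings stopped at sitting, so the two groups may not be alike in this respect. The Fidelity section uses this comparison for the intervention effect size, so the recording that enters it should be fixed in advance.

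**Working it through.** **Inputs.** From the sample size justification: 12 treated, 24 untreated, d = 1.0, alpha 0.05, power 80%. Sidedness is not stated; two-sided is assumed. The number of treated infants found sitting before the 9-month visit is not given anywhere, so a range is shown.

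**Formulas.** With n1 treated and n2 untreated, the noncentrality is d × √(n1·n2/(n1+n2)). The normal approximation to power is Φ(noncentrality − 1.960). The t-test power uses the noncentral t distribution with n1 + n2 − 2 degrees of freedom.

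**Step 1: reproduce the plan's figure.** For 12 v 24 the noncentrality is √(288/36) = √8 = 2.828. The normal approximation gives Φ(2.828 − 1.960) = Φ(0.868) = 80.7%, and the t-test gives 78.5%. One-sided versions give 88.2% and 87.0%, which do not match. The stated 80% is therefore reproduced, two-sided, with all 12 treated infants contributing.

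**Step 2: who has a 9-month value.** I take the visit at which sitting is found to be the last one recorded, which the text implies but does not spell out.

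| Treated infant | 9-month value? |
|---|---|
| Found sitting at a visit before the 9-month visit | No |
| First found sitting at the 9-month visit | Yes |
| Not sitting at the 9-month visit | Yes |

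**Step 3: power if some treated infants have no 9-month value.** All 24 untreated values are kept and d = 1.0. The numbers remaining are illustrative assumptions.

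| Treated with a value | Noncentrality | Power, normal | Power, t-test | d detectable at 80% (t-test) |
|---|---|---|---|---|
| 12 | √(288/36) = 2.828 | 80.7% | 78.5% | 1.02 |
| 10 | √(240/34) = 2.657 | 75.7% | 73.1% | 1.09 |
| 9 | √(216/33) = 2.558 | 72.5% | 69.8% | 1.13 |
| 6 | √(144/30) = 2.191 | 59.1% | 56.2% | 1.32 |

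**Step 4: if the untreated group loses the same share.** This is a further assumption. The t-test then gives 70.3% for 10 v 20, 65.3% for 9 v 18 and 46.8% for 6 v 12.

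**Step 5: power with one recording per infant.** If all 36 infants have a usable recording and d is still 1.0, power is 78.5% by t-test. A Mann-Whitney test gives about 76% (simulation with normal data, 20,000 runs: 76.0%).

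**The case against.** The best defence is that the 9-month wording is shorthand for the end of the intervention window. Data Collection names sitting onset or 9 months as the endpoint and explains why recordings after sitting are not wanted. On that reading no treated infant is lost and the table in Step 3 does not apply. This is plausible, but the power statement does not say it, and the two readings use different infants at different ages. One sentence would settle it.

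A second defence is that the analysis actually described is first visit against last visit. That Wilcoxon test uses each infant's own last visit and is unaffected. It is not, however, the comparison that the protocol calls primary and powers, and that comparison is missing from the statistics paragraph.

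Third, this is a 12-infant pilot, and the share lost is assumed rather than known. Both are true. They limit the weight of the point but do not remove the mismatch.

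A reader might infer more than the documents support:

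- **That every infant who sits before 9 months is lost.** With monthly visits, one who starts sitting after the 8-month visit can first be found sitting at the 9-month visit and is recorded there. For the same reason, the 9-month group is not made up only of non-sitters.
- **That the 80% is miscalculated.** It is reproduced in Step 1.
- **That most infants would be lost.** No figure supports any particular share.
- **That the bias favours, or works against, the intervention.** Without the untreated infants' recording ages and stopping rule, the direction cannot be given.

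**Conclusion.** The point holds in a limited form. Read as written, the protocol powers its primary comparison on 9-month values that its own stopping rule withholds for any treated infant found sitting at an earlier visit. The treated infants who remain are selected on motor progress.

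The size of the power loss is conditional. It is nil if no treated infant is found sitting early or if the endpoint reading was intended. It is about 5 percentage points if two are lost (78.5% to 73.1%) and about 22 if six are lost (78.5% to 56.2%). These figures assume a two-sided t-test, d = 1.0 and all 24 untreated values available. The possible bias is separate from the power loss, and its direction is unknown. The plan should be corrected, because the comparison is labelled primary and is meant to supply the intervention effect size.

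**What to change.** 1. **Sample size justification.** Replace the 9-month time point with each infant's last recording under the Data Collection rule: the visit where sitting is found, or 9 months, whichever is earlier. With monthly visits an infant may have been sitting for some weeks by then, and leg use changes with sitting. So add a sensitivity analysis that uses the last recording before sitting was found.
2. **Untreated infants.** Choose their recordings by the same rule. If their sitting status or endpoint recordings are not available, match on corrected age.
3. **Statistics paragraph.** Add the 12 v 24 comparison as a Mann-Whitney test, in line with the non-parametric choice already made, with adjustment for corrected age as a sensitivity analysis. Leave the Wilcoxon test as it is.
4. **Power.** State about 76% (Mann-Whitney) to 78% (t-test) for d = 1.0, and only on condition that all 36 infants have a usable recording.
5. **Fallback.** If no suitable untreated recordings exist, keep the 9-month comparison. Restate its power for the number of treated infants expected to have a 9-month value, and describe that group as infants not found sitting before the 9-month visit.

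**Cost.** The change is to wording and analysis, with no new visits. It does depend on what the existing untreated data contain: sitting dates alone are not enough without recordings at the matching point. Age at the endpoint will differ between infants and may itself be affected by treatment, which is why the age-adjusted result should remain a sensitivity analysis.

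### As written, at least 90% of the first-visit sensor recording follows the start of coaching, so the first-versus-last test compares two coached days rather than before with after

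*Combined protocol and SAP*

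**What the plan says.** All references are to the combined protocol and SAP.

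- **Title:** the study is framed as "Leg Movement Rate before and after a Caregiver- Provided Intervention".
- **Procedures:** consent is signed at the visit itself ("At the time of the visit, they will inspect all equipment and toys have any questions answered before signing the consent form"). On duration: "A caregiver will be present and engaged throughout the data collection visit, which lasts approximately 1 hour in their home". Families may choose the laboratory instead.
- **Data Collection, Sensor Data:** "infants will wear custom leg warmers with a pocket that securely holds a movement sensor at each ankle from the morning visit until bedtime". Caregivers take the sensors off at bedtime, some 10-12 hours later. On collection: "We will return to pick them up the next day".
- **Intervention:** "At each visit, the caregiver will be reminded of the infant's movement". The team then spends 15 minutes with the caregiver to "determine possible ways to achieve the goal of 1200 movements per hour of awake time". A logbook of exercises is also supplied at every visit.
- **Statistical analysis paragraph:** Wilcoxon signed-rank tests compare leg movement rate, adherence and the teaching-scale total between first and last visits.
- **Fidelity and Sample size justification:** the intervention effect size is to come from comparison with existing observational data. The planned primary comparison is 12 treated against 24 untreated infants.

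No section exempts the first visit from coaching, describes an uncoached sensor day, places coaching at the pick-up, or sets aside the hours after coaching.

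**The concern.** The coaching aims at the same quantity that the sensors record for the rest of that day. If the first recording is made mostly after coaching, it is not a pre-intervention value, and the study has none for leg movement rate. A report headed before and after would then describe the change from the first coached day. Any rise on the first day would sit inside the reference value and be lost from the reported change.

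This concerns leg movement rate only. The motor scale, the caregiver-teaching assessment and the 5-minute video are done during the visit and can precede coaching.

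**Working it through.** **1. The plan's own figure.** The only power statement is 80% for Cohen's d = 1.0 with 12 versus 24 infants. Noncentrality = 1/√(1/12 + 1/24) = 2.83. Two-sided at 0.05, the normal approximation gives power 0.807, and the t distribution with 34 df gives 0.785. The figure reproduces. It does not use the first-visit value, so this point leaves it unchanged.

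**2. Share of the first recording after coaching begins (w).** Inputs: wear time 10-12 h (Sensor Data) and visit about 1 h (Procedures). The order of sensor fitting and coaching is not stated, so both ends are shown.

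- Sensors on at the start and the whole visit hour counted as uncoached: 1 − 1/10 = 90.0%; 1 − 1/12 = 91.7%.
- Sensors fitted after coaching: 100%.

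The outcome is per awake hour, and awake hours are not given. Assuming 5, 6, 7 or 8 awake hours, with the full visit hour awake and uncoached, w = 80.0, 83.3, 85.7 or 87.5%. It is again 100% if the sensors go on afterwards.

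**3. What the test estimates.** Let B be the rate before any coaching and G the change built up over the months. Let p be the part of a same-day effect that comes from home practice, which the family keeps up. Let c be the further part that comes from having been coached that very day. Assume the parts add.

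| Arrangement | First day | Last day | Difference |
|---|---|---|---|
| As written | B + w(p + c) | B + G + p + wc | G + (1 − w)p |
| Sensor day before coaching, every visit | B | B + G + p | G + p |
| Only the first day changed | B | B + G + p + wc | G + p + wc |
| Coaching and home practice both absent on the two days | B | B + G | G |

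Under the current text, the total change from B to the last coached day is G + p + wc. The shortfall is (G + p + wc) − (G + (1 − w)p) = w(p + c), the coached share times the same-day effect. For that total-change estimand only, each 100 movements per awake hour of same-day effect would leave out 80 to 100 (w = 0.80 to 1.00).

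**4. Is there a size in the documents?** No same-day effect is given. The only same-day dose is the example strategy: 5 sets × 10 = 50 assisted kicks per diaper change. Assumed range:

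- 4 changes over 8 awake hours: 200/8 = 25 per hour (2.1% of 1200).
- 6 changes over 5 awake hours: 300/5 = 60 per hour (5.0% of 1200).

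This also assumes that both legs are counted together and that the software counts assisted movement; neither is stated. Any response by the infant, or other strategies, would add to it.

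**5. Why the two days must match.** Exact two-sided signed-rank test, n = 12, critical W = 13, size 0.042; normal differences, correlation 0.5, 200,000 simulations. Effect sizes and correlation are assumptions.

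- Both days coached alike, accumulated change 1.0 SD: power 0.85 whatever the same-day effect.
- First day uncoached, last day coached, no lasting change: rejection 0.082-0.107 for a same-day effect of 0.25 SD, and 0.215-0.315 for 0.5 SD (w from 0.80 to 1.00).
- Days matched, no lasting change: 0.042.

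**The case against.** The strongest reply is that nothing here makes the test wrong. Coaching at each visit means that the last day is coached too, so like is compared with like. Understatement appears only if the target is total change from before the intervention. The analysis paragraph itself speaks of first and last visits and never of a baseline. It also compares adherence at the first visit, which presupposes that the intervention is under way. The effect size is to come from untreated observational data. The reading is uncertain as well: being reminded of the infant's movement, and a logbook with pictures of the baby, fit a first visit poorly, so practice may have differed.

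Most of this stands, and it limits the point. It does not remove it: the title promises a before value, the text supplies no rule other than coaching at each visit, and the order within the visit cannot bring the coached share of wear time below 90%.

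The reply also has force against a careless remedy. Removing both coaching and home practice from the two days would recover none of the lost amount (last row of the table). Recording before that visit's coaching, while the family continues the home programme, does recover the practice part.

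A reader might infer more than the documents support:

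- *That the test loses power or is invalid.* For accumulated change it does not. Power falls only if the total is held at 1.0 SD and part of it is assigned to day 1 (about 0.63-0.64 with 25% and 0.36-0.37 with 50%). Those fractions are pure assumptions.
- *That a false benefit arises.* Under the current text it does not.
- *That a known amount is hidden.* The documents give no same-day effect.
- *That the 12-versus-24 comparison is biased.* It does not use the first-visit value.

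**Conclusion.** The point holds in limited form. On the plain text, 90-100% of the first-visit wear time (80-100% of awake time, assuming 5-8 awake hours) follows the start of coaching aimed at the measured variable. The first-versus-last test is sound for change between the first and last coached days, but it is not a before-after test. With a same-day effect in the intended direction, it understates the total change by the coached share times that effect. The effect's size is unknown; if it is zero, this source causes no bias. The error is conservative.

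The conclusion assumes that the intervention text applies to the first visit as written; a different actual order would change it. This is worth correcting because the affected value is the one the title calls before, but it does not threaten the planned primary comparison.

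**What to change.** 1. **State the order of sensor recording and coaching.** At every visit, complete the sensor day before that visit's coaching and logbook, for example by giving both at the next-day pick-up already planned. Content, length and monthly frequency of coaching stay as they are. The first value is then pre-intervention. The last is taken under the same order, with the home programme continuing but no coaching that day.
2. **Apply the same order at every visit, not the first alone.** Changing only the first day would add the same-day coaching effect to the contrast (step 5 of the working). The last visit depends on sitting onset and may not be known in advance, so one rule for all visits is the practical form.
3. **If data are already collected** (the analysis paragraph is in the past tense), state the order actually used. If coaching fell on the recording day, call the first value a first-intervention-day value and say that the total before-after change may be understated by an unknown amount.

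Cost: protocol wording, a pick-up contact at least 15 minutes longer with caregiver and infant present, and a defined arrangement for families who choose laboratory visits. For data already collected, the cost is a statement of the order used and, if needed, one label and one limitation sentence.
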